## 8.4 Treatment of Overdose

- For this study, any dose of M7824 greater than 2 times (i.e., > 2400 mg) than the planned dose administered within a 24-hour time period will be considered an overdose. Of note: In the dose-escalation study (EMR200647-001), participants safely received up to 30 mg/kg M7824 every 2 weeks (including those with doses > 2400 mg) with no observed maximum tolerated dose (refer to the IB). Safety at significantly higher doses has not been clinically evaluated.
- In case of overdose with clinical correlation, symptomatic treatment must be used; there are no known antidotes for the compound.
- In the event of an overdose, the study intervention infusion should be discontinued, and participants should be observed closely for any signs of toxicity. Supportive treatment should be provided if clinically indicated.
- Even if not associated with an AE or a SAE, any overdose is recorded in the CRF and reported to drug safety in an expedited manner. Overdoses are reported on a SAE Report Form, following the procedure in [Appendix 4](#), section on Reporting Serious Adverse Events.
- If an AE occurs resulting from an overdose, it should follow SAE reporting criteria as indicated in [Appendix 4](#).

## 8.5 Pharmacokinetics

- Whole blood samples of approximately 3.5 mL will be collected for measurement of serum concentrations of M7824. Collection times are specified in the Schedule of Activities (see Section 1.3; [Table 2](#)). The actual date and time (24-hour clock time) of each sample will be recorded to calculate actual time elapsed since the prior dose administration.
- The quantification of M7824 in serum will be performed using a validated assay method. Concentrations will be used to evaluate the PK of M7824.
- Remaining samples collected for analyses of M7824 concentration may also be used to evaluate immunogenicity and safety, or efficacy aspects related to concerns arising during or after the study.

- Details on processes for collection and shipment of these samples are in the Laboratory Manual. Retention time and possible analyses of samples after the end of study are specified in the respective ICF.
- PK and antidrug antibody (ADA) samples collected at the same time points may be used interchangeably if the dedicated sample has insufficient quantity as the participants will have consented to all collections and tests.
- PK samples will be collected according to [Table 2](#).

The following PK parameters will be estimated and reported in the PK Analysis Set:

- $C_{EOI}$
- $C_{trough}$ .

The PK parameters will be summarized using descriptive statistics. Individual as well as mean concentration-time plots will be depicted ([Table 6](#)).

The following PK parameters will be calculated, when appropriate.

**Table 6** **Pharmacokinetic Parameters**

Symbol	Definition
$C_{EOI}$	The concentration observed immediately at the end of infusion.
$C_{trough}$	The concentration observed immediately before next dosing (corresponding to pre-dose or trough concentration for multiple dosing).

CCI

Details on processes for collection and shipment of these samples are specified in the Laboratory Manual. The Sponsor will store the samples in a secure storage space with adequate measures to protect confidentiality. Retention time and possible analyses of samples after the end of study are specified in the respective ICFs.

## 8.9 Health Economics

Not applicable.

## 8.10 Immunogenicity Assessments

- Whole blood samples of approximately 5 mL will be collected for detection of antibodies against M7824 in serum. Collection times are specified in the Schedule of Activities (see Section 1.3; **Table 2**). Samples will be collected prior to any M7824 administration on the same study day.

## 9 Statistical Considerations

### 9.1 Statistical Hypotheses

The primary endpoint of the study is the confirmed OR according to RECIST 1.1, based on independent review of tumor assessments.

The following null hypothesis will be tested:

$$H_0: \text{ORR} \leq 10\%.$$

### 9.2 Sample Size Determination

The study aims at demonstrating an  $\text{ORR} > 10\%$  in the intention-to-treat (ITT) population by means of an exact binomial test.

The planned total sample size is 141 participants based on the following assumptions:

1. ORR of 18%
2. Alpha = 0.025 (1-sided) for the Exact test of the null hypothesis of an  $\text{ORR} \leq 10\%$ .

Under the given assumptions, the power to reject the null hypothesis at the primary analysis (PA) is 80%.

An observed ORR of 15.6% (22/141) would achieve a positive ORR outcome and would lead to an exact 95% CI of (10%, 22.7%).

The 2-sided 95% Clopper-Pearson CIs for different observed values for the ORR are provided in [Table 8](#).

**Table 8** Confidence Intervals for Different Objective Response Rates

N	N with CR/PR	ORR (%)	95% CI	
			Lower	Upper
141	15	10.6	6.1	16.9
	20	14.2	8.9	21.1
	21	14.9	9.5	21.9
	22	15.6	10.0	22.7
	25	17.7	11.8	25.1
	30	21.3	14.8	29.0
	35	24.8	17.9	32.8

CI=confidence interval, CR=complete response, N=number of participants, ORR=objective response rate, PR=partial response.

### Characterization of ORR in Individual BTC Subtypes

To characterize ORR in each individual BTC subtype (intrahepatic CCA, extrahepatic CCA and gallbladder cancer), subgroup analysis of ORR will be performed. With the planned overall sample size of 141 and assuming frequencies of 45% intrahepatic CCA, 30% extrahepatic CCA, and 25% gallbladder cancer, enrolment of at least 30 participants per subtype can be expected even in case the actual rate of participants with gallbladder cancer is below the assumed rate of 25%. A subgroup of 25% of the overall sample size of 141 participants would result in 35 participants.

*Risk of observing a high ORR in a subgroup by chance if true ORR is low ("H0")*

With a sample size of 30 participants and assuming a true ORR of 10%, the probability to observe at least 5 (16.7%) responders is 17.5%.

*Risk of observing a low ORR in a subgroup by chance if true ORR is 18% ("H1")*

With a sample size of 30 participants and assuming a true ORR of 18% (same as assumed for overall population), the probability to observe no more than 4 (13.3%) responders is 35.1%.

BTC subtype analyses are not powered for a formal statistical test, e.g., 30 participants would have 15.8% power to reject the null hypothesis of  $ORR \leq 10\%$ , using the same assumption of ORR of 18% and alpha = 0.025 (1-sided).

### Justification of the Assumption of a Confirmed ORR of 18%

M7824, as a monotherapy, has demonstrated promising clinical efficacy signal in 2L BTC. As of 20 March 2018, 30 participants with pretreated BTC received M7824 for a median duration of 8.9 weeks (range: 2 to 57.6 weeks); 5 participants remained on treatment. Seven participants had a confirmed OR (ORR, 23.3% by Investigator read and 20% by IRC, including 1 confirmation of response after data cutoff). Therefore, it is reasonable to assume that the confirmed ORR of M7824 in 2L BTC is 18% or higher.

**Justification of the Assumption of a Benchmark ORR of 10% to Define the Study Sample Size**

The benchmark for the ORR for 2L treatments is based on an update of a systematic review published in 2014 ([Lamarca 2014](#)) from available literature conducted in August 2018. Based on this updated review, which included 2L BTC studies reporting ORR results for chemotherapy alone or in association with an approved systemic anticancer therapy restricted to studies with > 20 participants (to avoid imprecise ORR estimates reported in smaller samples), 32 studies were identified reporting outcomes for 2137 participants globally.

The ORR estimate derived from these studies based on a regression model with a random effect was 7.2% with a 95% CI ranging from 5.5% to 9.2%. Using the upper limit of this CI we assumed the benchmark ORR to be 10%.

### **9.3 Populations for Analyses**

The analyses populations are specified below. The final decision to exclude participants from any analysis population will be made during a data review meeting prior to database lock.

For purposes of analysis, the analysis populations are defined in [Table 9](#).

**Table 9 Analysis Populations**

Screening (SCR)	All participants, who provided informed consent, regardless of the participant's study intervention status in the study.
Safety (SAF)/ Intention-to-treat (ITT)	All participants, who were administered at least 1 infusion of M7824. The primary analysis (PA) population for all analyses of efficacy, safety, and health-related quality of life is the Safety population.
Pharmacokinetic (PK)	All participants who complete at least 1 infusion of M7824, and who provide at least 1 sample with a measurable concentration of M7824.
Immunogenicity Analysis Set (IMM)	All participants who were administered at least 1 infusion of M7824 and have at least one valid antidrug antibody (ADA) result. All ADA analyses will be based on this analysis set.

### **9.4 Statistical Analyses**

#### **9.4.1 Efficacy Analyses**

##### **9.4.1.1 Analysis of Primary Endpoint**

The primary endpoint is confirmed OR according to RECIST 1.1, as determined by an IRC. For an OR of PR or CR, confirmation of the response according to RECIST 1.1 will be required no sooner than 4 weeks after the initial documentation of CR or PR. Confirmation of PR can be confirmed at an assessment later than the next assessment after the initial documentation of PR. The response at each scheduled tumor assessment and the OR will be listed for each participant. The number and proportion of OR (defined as CR + PR) will be tabulated. The ORR will be determined as the proportion of participants with a confirmed OR of PR or CR. The 95% CI for the ORR will be calculated using the Clopper-Pearson method. The test statistic of the exact

binomial test (1 sample) against the null hypothesis for the ORR will be calculated to determine whether the null hypothesis of an ORR  $\leq 10\%$  can be rejected.

Analysis of efficacy variables will also be performed on subgroup of interest, including but not restricted to

CCI

- PD-L1 expression

CCI

- MSI status

Further details will be specified in the integrated analysis plan (IAP).

#### 9.4.1.2                   Analysis of Secondary and CCI Endpoints

##### 9.4.1.2.1               Analysis of Secondary Endpoints

PFS according to RECIST 1.1, is defined as the time from first administration of study intervention until date of the first documentation of PD or death due to any cause in the absence of documented PD, whichever occurs first.

PFS data will be censored on the date of the last adequate tumor assessment for participants who do not have an event (PD or death), for participants who start new anticancer treatment prior to an event, or for participants with an event after two or more missing tumor assessments. Participants who do not have a baseline tumor assessment or who do not have any postbaseline tumor assessments will be censored on the date of first administration of study intervention unless death occurred on or before the time of the second planned tumor assessment, in which case the death will be considered an event.

Sensitivity analyses of PFS will be done including but not limited to:

- Alternative censoring rules including an analysis which counts death and progression according to RECIST 1.1 as PFS event regardless of the start of a new anticancer therapy and ignoring the number of missing evaluable tumor assessments before progression or death
- PFS as assessed by the Investigator

Details will be defined in the IAP.

DOR is defined, for participants with a confirmed OR, as the time from first documentation of OR (CR or PR) to the date of first documentation of objective PD or death due to any cause whichever occurs first. The censoring rules for DOR are as described above for PFS.

A durable response is defined as an OR (CR or PR) according to RECIST 1.1, determined by an IRC, with a duration of at least 6 months. Participants for whom the DOR is censored will be treated as failures (successes) in the analysis of durable response if the censored DOR is below (at least) 6 months. The DRR is defined as the percentage of participants with durable response. The 95% CI for the DRR will be calculated using the Clopper-Pearson method.

Overall survival (OS) is defined as the time from first administration of study intervention to the date of death due to any cause. Participants last known to be alive will be censored at date of last contact.

The Kaplan-Meier method will be used to estimate parameters for DOR, PFS, and OS. In particular, the PFS rate at 6 and 12 months will be estimated with corresponding 2-sided 95% CIs, and the survival rate at 6 and 12 months will be estimated with corresponding 2-sided 95% CIs. The CIs for the median will be calculated according to Brookmeyer and Crowley ([Brookmeyer and Crowley 1982](#)) and the CIs for the survival function estimates at the time points defined above will be derived using the log-log transformation according to Kalbfleisch and Prentice ([Kalbfleisch and Prentice 1980](#)). The estimate of the standard error will be computed using Greenwood's formula. The DOR, PFS, and OS will also be presented in participant listings.

The association between PD-L1 expression and efficacy endpoints – primarily ORR and DOR/DRR – will be analyzed. **CCI**

CCI

CCI

CCI

#### 9.4.2 Safety Analyses

The on-treatment period is defined as the time from the first study intervention administration to the last study intervention administration date + 30 days or the earliest date of subsequent anticancer drug therapy minus 1 day, whichever occurs first, unless otherwise stated.

Safety endpoints include AEs, clinical laboratory assessments, vital signs, physical examination, ECG parameters, and ECOG PS as described in Section 8.2.

## Adverse Events

All AEs will be coded according to the MedDRA. Severity of AEs will be graded using the NCI-CTCAE v5.0 toxicity grading scale.

The incidence of treatment-emergent adverse events (TEAEs), regardless of attribution, and TEAEs defined as possibly related to M7824 will be summarized by MedDRA preferred term and system organ class (SOC) and described in terms of intensity and relationship to M7824. TEAEs are those events with onset dates occurring during the on-treatment period or if the worsening of an event is during the on-treatment period. Any AEs with an onset or worsening date after the on-treatment period will be reported separately.

The incidence of SAEs and AESIs will be summarized by preferred term and SOC.

Descriptive statistics will be examined for indications of dose-related ADRs.

## Laboratory Variables

Laboratory results will be classified by grade according to NCI-CTCAE v5.0. The worst on-study grades after the first study intervention will be summarized. Shifts in toxicity grading from first treatment to highest grade will be displayed. Results for variables that are not part of NCI-CTCAE v5.0 will be presented as below, within, or above normal limits. Only participants with postbaseline laboratory values will be included in these analyses.

## Physical Examination (Including Vital Signs and 12-Lead ECGs)

Physical examination findings, including vital signs (body temperature, respiratory rate, heart rate, and blood pressure) and 12-lead ECGs, as indicated in the Schedule of Activities (Table 1) will be presented.

Further details will be provided in the IAP based on current safety experience applying the latest MedDRA version.

All safety analyses will be performed on the Safety Analysis population.

### 9.4.3 Other Analyses

Analysis of efficacy variables may be performed on subgroups of interest as needed. The detailed subgroups will be outlined in the IAP.

Serum concentrations of M7824 will be determined by a validated method at the times listed in the Schedule of Activities (Section 1.3; Table 2).

- Details on the PK, immunogenicity, and CCI [REDACTED] will be in the IAP that will be finalized before database lock. The PopPK analysis and exposure-response may be performed using combined data from several M7824 clinical studies and will be specified in a separate IAP. The PopPK, exposure-response and biomarker analyses will be presented separately from the main CSR.

### Estimation of Individual PK Parameters

- PK parameters will be calculated by the PK/PD Data Processing Group of QPD, Merck, Darmstadt, Germany, or by a CRO selected by the Sponsor.
- The statistical software SAS® (Statistical Analysis System, SAS-Institute, Cary NC, USA, windows version 9.4 or higher) may be used to produce tables, listings, and figures and in the calculation of PK parameters, if appropriate.

PK analyses ( $C_{EOI}$  and  $C_{trough}$ ) will be specified in the IAP finalized before database lock.

### ADA/Immunogenicity

Samples for ADA assessments will be collected as per the Schedule of Activities.

Immunogenicity testing strategy will be implemented and conducted in line with:

- Immunogenicity Assessment of Biotechnology-Derived Therapeutic Proteins (EMEA/CHMP/BMWP/14327/2006)
- Immunogenicity Assessment of Monoclonal Antibodies Intended for In Vivo Clinical Use (EMA/CHMP/BMWP/86289/2010)
- FDA Guidance for Industry: Assay Development for Immunogenicity Testing of Therapeutic Proteins (refer to FDA; December 2009, draft).

A validated method to detect ADAs in the presence of drug in human serum will be applied. The ADA titers of positive samples will be determined. Positive samples may be further evaluated for neutralizing capability. Individual participants will be categorized across all valid ADA results as ever-positive versus never-positive. ADA ever-positive participants will be further categorized as pre-existing, including treatment boosted, versus treatment emergent. ADA treatment-emergent participants will be further subdivided into transient positive and persistent positive.

Individual participants may be categorized across all valid neutralizing antibody results as ever-positive versus never-positive. Neutralizing antibody ever-positive participants may be further categorized as pre-existing versus treatment-emergent. Neutralizing antibody treatment-emergent participants may be further subdivided into transient positive and persistent positive.

Listings of drug concentration, TEAEs, and efficacy measures may be prepared for ADA ever-positive participants.

#### 9.4.4 Sequence of Analyses

There will be 2 data cutoff time points in this study:

- An **CCI** [REDACTED] per BTC subtype will be performed once 15 participants of each subtype have reached at least one postbaseline tumor assessment. Each subtype will be analyzed separately once criteria are met.
- The PA will be conducted 9 months after the accrual of the last of 141 planned participants.
- Second analysis for DRR and DOR will be conducted 15 months after the accrual of the last of 141 planned participants. The analysis will comprise a full evaluation of all efficacy and safety endpoints.

## 10

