- Safety Follow-up will continue until 12 weeks after the last dose of M7824. The 12-week Safety Follow-up is allowed to be conducted via telephone calls or patient chart reviews unless there is medical necessity requiring a clinical visit.
- Long-term Follow-up should be performed every 12 weeks after the Safety Follow-up according to the Schedule of Activities ([Table 1](#)). Long-term Follow-up should be performed by chart reviews or telephone calls.
- Survival Follow-up will continue until each participant was followed up for at least 3 years after the End-of-Treatment.

The overall study design is shown in [Figure 1](#). A detailed Schedule of Activities is provided in [Section 1.3](#).

[figure not shown]

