## 6 Overview of Planned Analyses

This IAP addresses the primary and second analyses for the global study as well as BTC subtype efficacy analysis. Additional statistical analysis plans for Independent Data Monitoring Committee (IDMC) will be developed separately.

All statistical analyses will be performed using cleaned eCRF data as well as external data including tumor assessment measured by the Independent Review Committee (IRC). All data used in the analysis will be included up to a data cut-off point.

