### 6.1 Primary and Second Analysis

Table 2 displays an overview of the primary and secondary analyses to be provided for this study.

**Table 2** Overview of Analyses

Analysis	Data cut-off point	Endpoints
Primary analysis (PA) at 9 Months	9 months after the first dose of the last of 141 planned participants	Full evaluation of all efficacy and safety endpoints. Plus, assessment of impact of COVID-19.
Second analysis at 15 Months	15 months after the first dose of the last of 141 planned participants	Full evaluation of all efficacy and safety endpoints

The timing of conduct of the primary and secondary analyses will be triggered by the data cut-off points displayed in Table 2 above and will evaluate all criteria described in this IAP.

CCI

## 7

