**Categorization of participants for COVID-19 impact assessment**

For the assessment of COVID-19 impact on this study, participants will be categorized as being affected by COVID-19 (either due to infection or due to circumstances of social distancing affecting the capabilities of sites/hospitals etc.) based on the COVID-19 study period defined as:

- The start of COVID-19 study period will be defined by country as the minimum of the date of the first death from COVID-19 occurred in each country according to the published data by European Centre for Disease Prevention and Control on 26th June 2020 and 11 March 2020 (WHO-start of world-wide pandemic).
- Post-pandemic could be defined as date (1) vaccination is released, (2) WHO declares COVID-19 pandemic over, (3) region-specific calls are made to end social distancing measures with no relevant rise in cases thereafter. As study treatment for the last participant started on 3rd January 2020, no participant will be grouped into the post COVID-19 study period for this study and no post-pandemic date will be defined.

Participants will be categorized into subgroups according to the methods shown in [Table 4](#) depending on the purpose of analysis.

**Table 4** Types of categorization for COVID-19 assessment

Type of categorization	Subgroup	Definition
Categorization for assessment on efficacy	Pre	Participant started treatment prior to and had progressive disease or died or withdrew from tumor assessments prior to COVID-19 study period
	During	Participant started treatment prior to or during COVID-19 study period and had any tumor assessments during the COVID-19 study period
	Post*	Participant started treatment post the COVID-19 study period
Categorization for assessment on safety without time window	Pre	Participant started treatment prior to COVID-19 study period
	During*	Participant started treatment during the COVID-19 study period
	Post*	Participant started treatment post the COVID-19 study period
Categorization for assessment on safety with time window	Pre	Participant started treatment 3 months prior to COVID-19 study period
	During	Participant started treatment on or after the date 3 months prior to COVID-19 study period
	Post*	Participant started treatment post the COVID-19 study period

\* No participants will be categorized into the 'post COVID-19 study period' or the 'during COVID-19 study period for safety without time window' for this study.

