## 14.8 Overall survival

Analysis (Analysis Population)	Derivation	Statistical Analysis Methods	Missing data handling
Secondary endpoint: Overall Response (OS)			
Secondary analysis (ITT)	Time from first administration of study treatment to the date of death due to any cause	Kaplan-Meier estimates (product-limit estimates) will be presented together with a summary of associated statistics (median time, 3-, 6-, 9-, 12-, 24-month rate estimates) including the corresponding two-sided 95% confidence intervals. The confidence intervals for the median will be calculated according to Brookmeyer and Crowley (1982) and confidence intervals for the survival function estimates at above defined timepoints will be derived using the log-log transformation according to Kalbfleisch and Prentice (2011) (conftype=loglog default option in SAS Proc LIFETEST). The estimate of the standard error will be computed using Greenwood's formula.	
For alive participants, OS will be censored at last date known to be alive
 
The following dates will be considered to determine the last date known to be alive (dates past the data cut-off will be ignored by the derivation; details provided in body text):
 

• All participant assessment dates

• Start and end dates of anticancer therapies administered after study treatment discontinuation.

• AE start and end dates

• Last known alive date collected on the 'Subject Status / Survival Follow-Up' eCRF page (do not use follow up date)

• Study drug start and end dates

 
Date of discontinuation from the "Study Termination" eCRF page (do not use if reason for discontinuation is lost to follow-up or death)

**Overall survival (OS)** is defined as the time from first administration of study treatment to the date of death due to any cause:

OS = (date of event or censoring – date of the first dose + 1)/30.4375 (months).

For participants alive at the time of data cut-off date or who are lost to follow up, OS will be censored at the last date known to be alive. The date of event / censoring is defined in [Table 6](#).

**Table 6** Survival Event / Censoring

Survival Status	Date of event/censoring	Censoring
Participants alive or lost to follow-up before or at cut-off date	Last date known to be alive	Yes
Participants who died before or at cut-off date	Date of death	No

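### No survival analysis is prespecified after the 15-month cut-off, although every participant is followed for at least 3 years after treatment ends

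*Protocol*

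**What the plan says.** Protocol 9.4.4 states that "There will be 2 data cutoff time points in this study". The two are: "The PA will be conducted 9 months after the accrual of the last of 141 planned participants", and "Second analysis for DRR and DOR will be conducted 15 months after the accrual of the last of 141 planned participants". An earlier look by BTC subtype, partly redacted, is listed in the same place. It is triggered by 15 participants per subtype with one post-baseline scan, so it adds nothing late.

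SAP 6.1 (Table 2) has the same two time points, the later being "15 months after the first dose of the last of 141 planned participants". It has both analyses evaluate every criterion in the SAP. SAP 6 sets the scope: "This IAP addresses the primary and second analyses for the global study as well as BTC subtype efficacy analysis". SAP 9 excludes data after a cut-off from cleaning, listings and summaries, apart from stop dates.

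Protocol 4.1 states: "Survival Follow-up will continue until each participant was followed up for at least 3 years after the End-of-Treatment". Protocol 4.4 ties the end of the study to the same milestone.

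For OS, SAP 14.8 requests "median time, 3-, 6-, 9-, 12-, 24-month rate estimates"; SAP 14.4 and 14.5 request the same landmarks for PFS and DOR. Protocol 9.4.1.2.1 asks only for the 6- and 12-month PFS and OS rates.

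**The concern.** OS is a secondary endpoint, and the long follow-up is collected to inform it. The amendment history for Protocol 4.0 (20 October 2020) gives survival data on participants with long-term benefit as the reason for revising the follow-up period. No planned analysis uses those later data.

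The dates suggest that the documents were not aligned. The SAP is version 2, dated 26 August 2020, before that protocol change. Protocol 5.0 is dated 22 June 2021, after both planned cut-offs would have passed, and still names only those two.

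Two things are at stake. The most complete OS result would have to be reported as unplanned, from a cut-off date chosen later. And the prespecified 24-month rate is requested at the two times when it is either not estimable or least well supported.

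**Working it through.** **The plan's own figure.** The only sizing figure is for ORR (Protocol 9.2). With N = 141 and H0 ORR ≤ 10%, the smallest count with a one-sided exact tail of at most 0.025 is 22. The exact alpha is 0.0239, and power at 18% is 0.8007. This matches the stated 80% and 22/141. No OS precision or number at risk is stated, so there is no OS figure to reproduce.

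**Inputs from the documents**
- Last first dose: 3 January 2020. SAP 9, COVID-19 categorization: "As study treatment for the last participant started on 3rd January 2020".
- Cut-offs: 9 and 15 months later, so about 3 October 2020 and 3 April 2021.
- Original protocol date: 8 November 2018, used as an outer bound for the first dose. The actual first-dose date is not given.
- One month = 30.4375 days (SAP 9).

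**Assumptions.** Uniform accrual from the first to the last first dose; exponential OS with a median of 6, 9 or 12 months. The documents give no second-line median OS; Protocol 2.2 says only that median survival on chemotherapy for unresectable disease is under 1 year.

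**Step 1: unanalysed follow-up.** End-of-Treatment for the last participant cannot precede 3 January 2020, so 3 years of follow-up cannot end before 3 January 2023. From 3 April 2021 to 3 January 2023 is 21.0 months.

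**Step 2: longest possible follow-up**
- 8 November 2018 to 3 October 2020 = 22.8 months. This is below 24, so nobody can be at risk at 24 months at the primary analysis. No survival assumption is needed. The same holds for PFS, and for DOR, whose clock starts later, at response.
- 8 November 2018 to 3 April 2021 = 28.8 months. Only participants dosed by about 3 April 2019 can reach 24 months.

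**Step 3: number at risk for OS at 24 months, 15-month cut-off**

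Number with 24 months of potential follow-up = 141 × (longest follow-up − 24) / accrual length. Expected number at risk = that number × S(24), with S(24) = 0.5^(24/median). S(24) is 0.0625, 0.157 and 0.25 for medians of 6, 9 and 12 months. Results use unrounded inputs.

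| First dose | Accrual (months) | Longest follow-up (months) | With 24 months' potential | At risk, median 6 / 9 / 12 |
|---|---|---|---|---|
| 8 Nov 2018 | 13.8 | 28.8 | 49.1 | 3.1 / 7.7 / 12.3 |
| 1 Feb 2019 | 11.0 | 26.0 | 25.8 | 1.6 / 4.1 / 6.5 |
| 1 Mar 2019 | 10.1 | 25.1 | 15.3 | 1.0 / 2.4 / 3.8 |
| 1 May 2019 | 8.1 | 23.1 | 0 | 0 / 0 / 0 |

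These are expected counts, and simulation of the first three rows agrees with them. In the most favourable case (8 November 2018, median 12) the mean was 12.4, with 95% of simulated trials between 6 and 19.

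**Step 4: once all have 24 months of potential follow-up (from about 3 January 2022).** 141 × 0.0625 = 8.8; 141 × 0.157 = 22.2; 141 × 0.25 = 35.2.

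**The case against.** A reader might infer that the plan permits only two cut-offs, that the 3-year follow-up is never analysed, and that the 24-month rate always rests on almost nobody. The documents do not support this. Protocol 9.4.4 says what will happen and forbids nothing further. Protocol Appendix 2 foresees a clinical study report after study completion, and SAP 4 allows unplanned analyses in that report if they are labelled. Survival data up to about April 2021 are analysed in full. Nobody at risk at 24 months is certain only at the 9-month cut-off; at 15 months it depends on inputs that the documents do not give.

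Four further arguments carry weight.
- The protocol's own landmarks are covered. At the second cut-off every participant has at least 15 months of potential follow-up, so 12-month OS is fully supported. OS carries no hypothesis test.
- A misleading 24-month figure is unlikely to pass unnoticed. SAP 9 shows statistics that cannot be calculated as not determined, SAP 14.8 presents numbers at risk, and SAP 14.9 and 14.10 report follow-up time.
- The precision loss can be modest. With uniform accrual over about 14 months, the simulated standard deviation of the 24-month OS estimate at 15 months is about 3.3 to 3.4 points at a median of 8 months, against √(0.125 × 0.875/141) = 2.8 points with complete follow-up. At a median of 11 months it is 4.1 against 3.5. Slower early accrual makes it worse.
- The SAP predates Protocol 4.0, so it could not reflect that change, and a later SAP version may exist.

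These arguments limit the consequence without removing the gap. Neither the study report nor the post-hoc clause sets a cut-off or prespecifies an OS analysis, and Protocol 5.0 could have added one.

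**Conclusion.** The point holds in a limited form: no analysis of survival data beyond the 15-month cut-off is prespecified, and at least 21 months of required follow-up lie beyond it. This assumes that participants are followed as Protocol 4.1 requires; deaths and withdrawals would shorten the collection.

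That the 24-month OS, PFS and DOR rates have nobody at risk at the primary cut-off follows from dates alone. If the last of the 141 planned participants was dosed before 3 January 2020, both cut-offs move earlier and support is weaker still. The 15-month range for OS (about 0 to 12 at risk, against about 9 to 35) rests on the accrual and survival assumptions above, and its upper end needs dosing to have begun on the day the original protocol was dated.

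The primary ORR test and the 6- and 12-month OS rates stand. This is a cheap improvement to the secondary OS reporting, not a threat to the trial's main conclusion.

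**What to change.** Add to Protocol 9.4.4 and SAP 6.1 a prespecified final OS cut-off at the end of survival follow-up, and report the 24-month OS rate there with the existing OS programs. Omit the 24-month OS, PFS and DOR rates from the 9-month outputs. Keep them at 15 months, with the number at risk beside each estimate.

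The cost is one more round of data cleaning, one more cut-off and rerun, and changes to the protocol and SAP wording. The survival data are already being collected.
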